3.5.2 End of Study

Primary Completion: The primary completion date is defined as the date when the last subject is assessed or receives an intervention for the final collection of data for the primary endpoint(s), whether the study concluded as planned in the protocol or was terminated early.

If the study concludes prior to the primary completion date originally planned in the protocol (ie, early termination of the study), then the primary completion will be the date when the last subject is assessed or receives an intervention for evaluation in the study (ie, last subject last visit).

The primary completion date is the date when data for the primary endpoint are last collected for the purposes of conducting the primary analysis.

End of Study: The end of study date is defined as the date when the last subject across all sites is assessed or receives an intervention for evaluation in the study (ie, last subject last visit), following any additional parts in the study (eg, long-term follow-up) as applicable.

4. SUBJECT ELIGIBILITY

Investigators will be expected to maintain a screening log of all potential study candidates that includes limited information about the potential candidate (eg, date of screening).

Before any study-specific activities/procedure, the appropriate written informed consent must be obtained (see Section 11.1).

4.1 Inclusion Criteria

In order to be eligible for participation in this trial, the subject must meet the following criteria:

101. Subject/legally acceptable representative has provided written informed consent prior to initiation of any study-specific procedures.
102. Age \geq 18 years at the time of informed consent
103. Have histologically confirmed DLBCL that is either:
 - Refractory after at least 1 regimen of systemic chemotherapy and/or targeted therapy, and refractory is defined as progressive or stable disease as the best response to the most recent systemic chemotherapy regimen or disease progression or relapse within 12 months after autologous stem cell transplantation; when using PET for assessment, for subjects with refractory disease and who have received radiotherapy, PET positivity should be demonstrated no less than 6 weeks after the last dose of radiotherapy (Crump et al, 2017; Neelapu et al, 2017; Cheson et al, 2007), or
 - In first or later relapse if have received at least 2 systemic regimens since time of diagnosis, or
 - Relapsed post-autologous or allogeneic HSCT with adequate organ function after proximity to transplantation time exclusions as specified in Exclusion Criteria 208 and 209
104. Have measurable disease defined as at least 1 lesion that can be accurately measured in at least 2 dimensions with spiral computed tomography (CT) scan. Minimum measurement must be either $>$ 15 mm in the longest diameter OR $>$ 10 mm in the short axis.
105. Demonstrate adequate organ function as defined in Table 4-1.

Table 4-1. Adequate Organ Function Laboratory Values

System	Laboratory Value
Hematological	
Absolute neutrophil count (ANC)	≥ 1,500/mcL
Platelets	≥ 100,000/mcL
Hemoglobin	≥ 9 g/dL or ≥ 5.6 mmol/L
Renal	
Creatinine OR Measured or calculated ^a creatinine clearance (CrCl) (glomerular filtration rate (GFR) can also be used in place of creatinine or CrCl)	≤ 1.5xULN OR ≥ 60 mL/min for subject with creatinine levels >1.5 x institutional upper limit of normal (ULN)
Hepatic	
Total bilirubin	≤ 1.5xULN OR Direct bilirubin ≤ ULN for subjects with total bilirubin levels > 1.5 x ULN
AST (SGOT) and ALT (SGPT)	≤ 2.5xULN OR ≤ 5xULN for subjects with liver metastases
Coagulation	
International Normalized Ratio (INR) or Prothrombin Time (PT) Activated Partial Thromboplastin Time (aPTT)	≤ 1.5xULN unless subject is receiving anticoagulant therapy as long as PT or PTT is within therapeutic range of intended use of anticoagulants ≤ 1.5xULN unless subject is receiving anticoagulant therapy as long as PT or PTT is within therapeutic range of intended use of anticoagulants

ALT = alanine aminotransferase; AST = aspartate aminotransferase; SGOT = serum glutamic oxaloacetate transaminase; SGPT = serum glutamate pyruvate transaminase; ULN = upper limit of normal

^a Creatinine clearance should be calculated per institutional standard.

106. Have resolution of toxic effect(s) of the most recent prior chemotherapy to grade 1 or less (except alopecia). If subject received major surgery or radiation therapy of > 30 Gy, they must have recovered from the toxicities and/or complications of the intervention(s).
107. Female subjects of childbearing potential (Section 6.10.1) must have a negative urine or serum pregnancy test within 72 hours prior to receiving the first dose of study medication. If the urine test is positive or cannot be confirmed as negative, a serum pregnancy test will be required.
108. Female subjects of childbearing potential must be willing to use an adequate method of contraception as outlined in Section 6.10.1 for the course of the study through 120 days after the last dose of study medication.

Note: Abstinence is acceptable if this is the usual lifestyle and preferred contraception for the subject.

109. Male subjects must agree to use an adequate method of contraception as outlined in Section 6.10.2, starting with the first dose of study therapy through 120 days after the last dose of study therapy.

Note: Abstinence is acceptable if this is the usual lifestyle and preferred contraception for the subject.

110. Eastern Cooperative Oncology Group (ECOG) performance status ≤ 2
111. Life expectancy of ≥ 12 weeks in the opinion of the Investigator
113. Biopsy proven DLBCL (biopsy proven at least at primary diagnosis of DLBCL), including DLBCL that represents transformation of indolent NHL (including follicular, marginal zone, and lymphoplasmacytic lymphoma excluding chronic lymphocytic leukemia or Hodgkin Lymphoma) are eligible. Subjects with transformation of indolent lymphoma must have received therapy after a diagnosis of transformation that is appropriate for aggressive histology.

4.2 Exclusion Criteria

Subjects meeting any of the following exclusion criteria will not be eligible to participate in this study:

201. Richter's transformation (DLBCL arising in the setting of prior chronic lymphocytic leukemia) or PMBCL
202. History or presence of clinically relevant CNS pathology such as epilepsy, paresis, aphasia, stroke, severe brain injury, dementia, Parkinson's disease, cerebellar disease, organic brain syndrome, or psychosis.
203. Has disease that is suitable for local therapy administered with curative intent.
204. Currently receiving treatment in another investigational device or drug study, or less than 30 days since ending treatment on another investigational device or drug study(s). Thirty days is calculated from day 1 of protocol-specified therapy
205. Has a diagnosis of immunodeficiency or has received systemic steroid therapy (in excess of 10 mg daily of prednisone equivalent) or any other form of immunosuppressive therapy within 7 days prior to the first dose of protocol specified therapy.
206. Has had a prior anticancer mAb within 30 days prior to first day of study treatment or who has not recovered (ie, \leq grade 1 or at baseline) from adverse events due to such agents administered more than 30 days earlier.
207. Has had prior chemotherapy, targeted therapy, or radiation therapy within 14 days prior to first day of study treatment or who has not recovered (ie, \leq grade 1 or at baseline) from adverse events due to such previously administered agents.

Note: Subjects with \leq grade 2 neuropathy or \leq grade 2 alopecia are an exception to this criterion and may qualify for the study.

208. Has undergone prior allogeneic HSCT:
- within the last 5 years
- OR
- greater than 5 years ago but has active graft versus host disease (GvHD) requiring systemic treatment.
209. Has received autologous HSCT within 6 weeks prior to start of treatment.
211. History of other malignancy within the past 3 years with the exception of:
- Malignancy treated with curative intent and with no known active disease present for ≥ 3 years before enrollment and felt to be at low risk for recurrence by the treating physician
 - Adequately treated non-melanoma skin cancer or lentigo maligna without evidence of disease
 - Adequately treated cervical carcinoma in situ without evidence of disease
 - Adequately treated breast ductal carcinoma in situ without evidence of disease
 - Prostatic intraepithelial neoplasia without evidence of prostate cancer
 - Adequately treated urothelial papillary noninvasive carcinoma or carcinoma in situ
212. Has known active CNS metastases and/or carcinomatous meningitis; brain magnetic resonance imaging (MRI) is preferred for CNS disease assessment for all patients at screening; if MRI is contraindicated (eg, pacemaker, implant, et al) a CT can be performed.
- Note: Subjects with previously treated CNS metastases may participate provided they are stable (without evidence of progression by imaging [using the identical imaging modality for each assessment, either MRI or CT scan] for at least 28 days prior to the first dose of trial treatment and any neurologic symptoms have returned to baseline), have no evidence of new or enlarging CNS metastases, and are not using steroids for at least 7 days prior to protocol specified therapy. This exception does not include carcinomatous meningitis which is excluded regardless of clinical stability.*
213. Has active autoimmune disease that has required systemic treatment in past 2 years (ie, with use of disease modifying agents, corticosteroids or immunosuppressive drugs).
- Note: Replacement therapy (eg, thyroxine, insulin, or physiologic corticosteroid replacement therapy for adrenal or pituitary insufficiency, etc.) is not considered a form of systemic treatment.*
214. Has a history of (non-infectious) pneumonitis that required steroids or current pneumonitis
215. Has a history of interstitial lung disease
216. Has an uncontrolled active infection requiring systemic therapy
217. Is pregnant or breastfeeding, or expecting to conceive or father children within the projected duration of the trial, starting with the screening visit through 120 days after the last dose of trial treatment.

218. Has received prior therapy with an anti-PD-1, anti-PD-L1, or anti-PD-L2 agent or if the subject has previously participated in Merck MK-3475 (pembrolizumab) clinical trials.
219. Has received prior anti-CD19 directed therapy.
220. Known hypersensitivity to Igs or any other component of the study drugs formulation.
221. Has a known history of Human Immunodeficiency Virus (HIV) (HIV 1/2 antibodies).
222. Has chronic or active Hepatitis B (eg, hepatitis b surface [HBs] antigen reactive or quantifiable hepatitis b virus [HBV] viral load) or Hepatitis C (eg, hepatitis c virus [HCV] RNA [qualitative] is detected).
224. Has received a live vaccine within 30 days of planned start of protocol specified therapy.
225. Subject likely to not be available to complete all protocol-required study visits or procedures, and/or to comply with all required study procedures to the best of the subject's and/or investigator's knowledge.
226. History or evidence of any other clinically significant disorder, condition or disease (with the exception of those outlined above) that, in the opinion of the investigator or Amgen physician, if consulted, would pose a risk to subject safety or interfere with the study evaluation, procedures or completion.
227. Has a history of solid organ transplantation.
228. Biopsy proven DLBCL with substantial occurrence of malignant cells into the bloodstream (lymphocyte count $\geq 7 \times 10^9/L$) including all leukemic presentations, even though with acceptable histologies.

5. SUBJECT ENROLLMENT

Before subjects begin participation in any study-specific activities/procedures, Amgen requires a copy of the site's written institutional review board/independent ethics committee (IRB/IEC) approval of the protocol, informed consent form (ICF), and all other subject information and/or recruitment material, if applicable (see Section 11.2). All subjects or legally acceptable representatives must personally sign and date the ICF before commencement of study-specific activities/procedures.

A subject is considered enrolled when the investigator decides that the subject has met all eligibility criteria and Amgen confirms the enrollment. The investigator is to document this decision and date in the subject's medical record and in/on the enrollment case report form (CRF).

Each subject who enters into the screening period for the study (entry is defined as the point at which the subject signs the informed consent) receives a unique subject identification number before any study-related activities/procedures are performed. The subject identification number will be assigned manually. This number will be used to

identify the subject throughout the clinical study and must be used on all study documentation related to that subject.

Subjects who are unable to complete or meet eligibility at the initial screening will be permitted to re-screen twice. Re-screen subjects must first be registered as a screen failure manually and subsequently registered as re-screen. Once the subject is registered as re-screened, a new 21 day screening window will begin. Subjects will retain the same subject identification number assigned at the original screening.

Subjects re-screening within 21 days of the signing of the original informed consent only need to repeat the assessment(s) that did not originally meet the eligibility criteria; all other initial screening assessments do not need to be repeated. Subjects re-screening greater than 21 days from the signing of the original informed consent must be re-consented and repeat all screening procedures per the protocol.

The subject identification number must remain constant throughout the entire clinical study; it must not be changed after initial assignment, including if a subject is rescreened.

Subjects should initiate protocol-specified therapy within 5 days of enrollment confirmation.

6. TREATMENT PROCEDURES

The investigational products for this study are blinatumomab and pembrolizumab. Blinatumomab will be manufactured and packaged by Amgen, Inc. and distributed using Amgen clinical study drug distribution procedures. Pembrolizumab will be labeled, packaged, and distributed by Amgen (or designee) using Amgen (or designee) clinical study drug distribution procedures. Pembrolizumab is supplied as pembrolizumab 100 mg/4 mL vials (25 mg/mL) solution for IV infusion. Additional details regarding the pembrolizumab product are provided in the investigational product instruction manual (IPIM).

The term protocol-specified therapies used throughout the protocol refers to blinatumomab and pembrolizumab. It does not refer to other protocol-mandated medication (eg, pre-phase treatment with dexamethasone).

All other protocol-mandated therapies, including pre-phase therapies, that are commercially available are not provided or reimbursed by Amgen (except if required by local regulation). The investigator will be responsible for obtaining supplies of these protocol-mandated therapies.

6.1 Classification of Product(s) and/or Medical Device(s)

The Amgen investigational product used in this study is blinatumomab.

The non-Amgen investigational product used in this study is pembrolizumab.

The IPIM, a document external to this protocol, containing detailed information regarding the storage, preparation, and administration of blinatumomab and pembrolizumab will be provided to each investigational site.

Non-investigational medical device(s) (ie, medical device(s) not under study) or products will be described in Section 6.7.

6.2 Investigational Product

6.2.1 Amgen Investigational Product: Blinatumomab

Blinatumomab will be supplied as 4 mL single-use glass injection vials containing a sterile, preservative-free, white to off-white, lyophilized powder for IV infusion following reconstitution with sterile water for injection. Sterile water for injection and supplies required for reconstitution and injection of blinatumomab will not be provided to clinical sites.

To prepare blinatumomab for CIVI, the lyophilized powder is reconstituted with sterile water for injection. The reconstituted solution is added to an infusion bag containing 0.9% NaCl and a product-specific stabilizer (IV Solution Stabilizer). The IV solution stabilizer functions to prevent adsorption of blinatumomab to surfaces of the infusion components. The IV Solution Stabilizer is supplied in 10 mL single-use glass injection vials as a sterile, preservative-free, clear, colorless-to-slightly-yellow liquid concentrate.

For information surrounding the use of a continuous infusion pump, refer to Section 6.7.

6.2.1.1 Blinatumomab Dosage, Administration, and Schedule

Blinatumomab is administered as a CIVI. The infusion bags will be changed by site nursing or home health care personnel trained on the protocol and on the proper administration of blinatumomab.

The first cycle of blinatumomab treatment consists of 8 weeks (56 days) of standard blinatumomab continuous infusion. Please refer to the study schema (Figure 1).

The first cycle is followed by a 28-day (\pm 3 days) blinatumomab treatment-free interval. Those subjects who do not meet criteria for discontinuation after the blinatumomab treatment-free interval may then receive a consolidation cycle of blinatumomab (cycle 2) consisting of 28 days standard blinatumomab continuous infusion. In both cycle 1 and

the consolidation cycle, the initial dose of blinatumomab will be 9 µg/day and will be dose escalated at 7-day intervals until the target dose is reached.

The dosing and schedule will be as outlined in Section 7.

The drug administration should not be interrupted, if possible. In case of infusion interruption, due to any technical or logistic reason, the interruption should be as short as possible and the infusion restarted at the earliest time possible. Every interruption longer than 1 hour should be documented. Administration of dexamethasone premedication will occur as described in Section 6.3. In case the infusion is interrupted in the first cycle and/or the second cycle, the total days at the target dose should be at least 85% of the planned days, but no more than the planned days.

A dose of up to 10% higher than the intended blinatumomab dose (per day) may not require specific intervention. In case of overdose or medication error, the infusion should be immediately stopped. Routine supportive and symptomatic care according to standard medical practice is recommended. Once the subject is stabilized and no clinically relevant safety findings due to blinatumomab are observed, resumption of blinatumomab at a correct dose can be considered after consultation with the Amgen medical monitor.

For blinatumomab, a dose of greater than 10% higher than the intended dose will be considered clinically important and classified as a serious adverse event under the criterion of “other medically important serious event” per Section 9.1.3. If the overdose results in additional adverse event/s, the subject should be followed carefully until all signs of toxicity are resolved and the adverse event/s should be recorded/reported per Section 9.2 of the protocol.

The dose, start and stop date/time, and lot number of protocol-specified therapy is to be recorded on each subject’s CRF.

Refer to the Blinatumomab Investigational Brochure for further information.

6.2.1.2 Blinatumomab Inpatient Dosing

Subjects are required to be monitored in a hospital for a minimum of 72 hours following initiation of therapy and for a minimum of 48 hours at each step dose increase. Close monitoring is indicated because of the potential adverse events associated with T cell redistribution and potential cytokine release effects triggered by the administration of blinatumomab. Nurses/physicians familiar with such conditions should be available for immediate intervention in case of complications.

Also, if blinatumomab is interrupted for longer than 4 hours, re-start of the infusion should be performed in the hospital, under the supervision of the investigator. The subject should be observed overnight for possible side effects after the re-start, either in the hospital or in the outpatient setting as applicable. Administration of dexamethasone premedication will occur as described in Section 6.3.

6.2.1.3 Blinatumomab Outpatient Dosing

Apart from the situations where inpatient dosing is required per Section 6.2.1.2, and if a subject is deemed stable by the investigator, blinatumomab infusion may continue as an outpatient. Twenty-four-hour emergency on-call service must be ensured in the outpatient setting.

In the outpatient setting, either the subject will return to the study site for changes of infusion bags or the subject will be visited by a well-trained ambulant/home care service provider at specific intervals to change the infusion bag. The subject and the ambulant/home care provider will be trained and will receive written instructions for storage of the IV bags.

For the ambulant/home care provider study-specific requirements and recording of source documentation must be completed before any study-related tasks are started. The date and time of infusion bag changes, all infusion start and stop times, and any dose modifications should be recorded accurately.

A comprehensive list of all home care services, including but not limited to the storage, handling, and administration of blinatumomab as well as mandatory procedural and data collection requirements will be separately provided in a home health care manual.

Following each visit, this information will be documented on the Ambulant/Home Care Services visit worksheet and forwarded to the investigator. Any unexpected or unusual events as well as any deviations will be communicated promptly to the investigator. The ambulant/home care professionals must provide 24-hour emergency on-call service. In addition, the subject will visit the study site for the examinations according to the Schedule of Assessments (Table 7-1, Table 7-2, Table 7-3, and Table 7-4).

6.2.1.4 Dosage Adjustments, Delays, Rules for Withholding or Restarting, Permanent Discontinuation for Blinatumomab

6.2.1.4.1 Infusion Interruption/Dose Modification Due to Adverse Events for Blinatumomab

Common Terminology Criteria for Adverse Events (CTCAE v 4.0) grade 4 adverse events at least possibly related to blinatumomab will require that the administration of

blinatumomab be stopped until the adverse event has recovered to CTCAE grade 1 or baseline.

Table 6-1. Blinatumomab Discontinuation and Stopping Rules

Toxicity	Grade	Instructions for Treatment Interruption and Re-start
Cytokine Release Syndrome (CRS)	3	
 •Interrupt blinatumomab until the event improves to grade ≤ 1 and administer corticosteroids (refer to Table 6-4) •Restart no less than 72 hours after the initial observation of the grade 3 event at the following dose levels: 
 ○ If the event occurred at 56 or 112 $\mu\text{g}/\text{day}$, resume at 28 $\mu\text{g}/\text{day}$ ○ If the event occurred at 28 $\mu\text{g}/\text{day}$, resume at 9 $\mu\text{g}/\text{day}$ •Escalate up 1 dose level after 7 days if toxicity does not reoccur. Increase dose stepwise at 7-day intervals to target dose of cohort (28 $\mu\text{g}/\text{day}$ for cohort Ia, 56 $\mu\text{g}/\text{day}$ for cohort IIa, 112 $\mu\text{g}/\text{day}$ for cohort IIIa) if toxicity does not reoccur. •Permanently discontinue if: 
 ○ Initial grade 3 CRS does not improve to grade ≤ 1 within 7 days, OR ○ Grade 3 CRS reoccurs at the lower dose level within 7 days of re-initiation OR ○ Grade 3 CRS reoccurs at a dose of 9$\mu\text{g}/\text{day}$ without prior step-dose escalation.
	4	
 •Permanently discontinue blinatumomab
Neurologic Events	3	
 •Interrupt blinatumomab until the event improves to grade ≤ 1 and administer corticosteroids (refer to Table 6-4) •Restart no less than 72 hours after the initial observation of the grade 3 event at the following dose levels: 
 ○ If the event occurred at 56 or 112 $\mu\text{g}/\text{day}$, resume at 28 $\mu\text{g}/\text{day}$ ○ If the event occurred at 28 $\mu\text{g}/\text{day}$, resume at 9 $\mu\text{g}/\text{day}$ •Escalate up 1 dose level after 7 days if toxicity does not reoccur. Increase dose stepwise at 7-day intervals to target dose of cohort (28 $\mu\text{g}/\text{day}$ for cohort Ia, 56 $\mu\text{g}/\text{day}$ for cohort IIa, 112 $\mu\text{g}/\text{day}$ for cohort IIIa) if toxicity does not reoccur. •Permanently discontinue if: 
 ○ Initial grade 3 neurologic event occurred at 9 $\mu\text{g}/\text{day}$, OR ○ Initial grade 3 neurologic event does not improve to grade ≤ 1 within 7 days, OR ○ Grade 3 neurologic event reoccurs at the lower dose level within 7 days of re-initiation, OR ○ Grade 3 neurologic event reoccurs at a dose of 9 $\mu\text{g}/\text{day}$
	4	
 •Permanently discontinue blinatumomab
	Seizure ^a Grade ≥ 2	
 •Interrupt blinatumomab, administer corticosteroids (refer to Table 6-4) and anti-seizure medication per local practice •For restart, refer to grade 3 neurologic events above for dose level rules for re-instituting infusion •Do not re-initiate blinatumomab until 7 days after the last seizure and after therapeutic levels of anti-seizure medication are likely to have been achieved and documented •Permanently discontinue if a second seizure occurs with re-initiation of blinatumomab at any dose

Footnotes defined on the next page of the table

Table 6-1. Blinatumomab Discontinuation and Stopping Rules

Toxicity	Grade	Instructions for Treatment Interruption and Re-start
Elevated Liver Enzymes		
 • Interrupt blinatumomab if any one of the following occurs: 
 ○ TBL > 3 x ULN at any time ○ ALP > 8 x ULN at any time ○ AST or ALT > 8 x ULN at any time ○ AST or ALT > 5 x ULN but < 8 x ULN for ≥ 14 days ○ AST or ALT > 3 x ULN with clinical signs or symptoms that are consistent with hepatitis (eg, right upper quadrant abdominal pain/tenderness, fever, nausea, vomiting, jaundice) • Permanently discontinue blinatumomab if: 
 ○ TBL > 2 x ULN OR INR >1.5 (for subjects not on anticoagulant therapy) 
AND
 
 ○ AST or ALT > 3x ULN (when baseline was <ULN) 
AND
 
 ○ no other cause for the combination of the above laboratory abnormalities is immediately apparent 
 • Refer to Section 6.4 for additional detail
Other Clinically Relevant Adverse Events	3	
 • Interrupt blinatumomab until event improves to grade ≤1 • Restart no less than 72 hours after the initial observation of the grade 3 event at the following dose levels: 
 ○ If event occurred at 56 or 112 µg/day, resume at 28 µg/day ○ If event occurred at 28 µg/day, resume at 9 µg/day • Escalate up 1 dose level after 7 days if toxicity does not reoccur. Increase dose stepwise at 7-day intervals to target dose of cohort (28 µg/day for cohort Ia, 56 µg/day for cohort IIa, 112 µg/day for cohort IIIa) if toxicity does not reoccur. • Permanently discontinue blinatumomab if: 
 ○ Initial grade 3 event does not improve to grade ≤ 1 within 14 days, (with the exception of delay in restart due to logistical difficulties, in which case the restart may be postponed for an additional 7 days) 
OR
 
 ○ Grade 3 event reoccurs at the lower dose level within 7 days of re-initiation, OR ○ Grade 3 event reoccurs at a dose of 9 µg/day without prior step-dose escalation
	4	
 • Permanently discontinue blinatumomab

Page 2 of 2

ALP = alkaline phosphatase; ALT = alanine aminotransferase; AST = aspartate aminotransferase; INR = international normalized ratio; MRI = magnetic resonance imaging; TBL = total bilirubin; ULN = upper limit of normal

^a Obtain brain MRI and perform cerebrospinal fluid (CSF) analysis, if there are no contraindications.

Subjects who have been dose reduced will have an option to re-escalate to higher dose levels within their assigned dose cohort once the adverse event has resolved to grade 1 or less for at least 7 days. (See [Appendix F](#)).

Re-start of the infusion should be performed in the hospital, under supervision of the investigator. Before blinatumomab is re-started, premedication with dexamethasone must be administered as described in [Table 6-4](#). The subject should be observed overnight for possible side effects after each restart, either in the hospital or in the outpatient setting, as applicable. When the blinatumomab infusion is re-started per [Table 6-1](#) guidelines, the schedule of assessment procedures should be repeated to align with the re-started blinatumomab dose. If re-start is at 9 µg/d then repeat schedule of assessments starting at D1. If re-start is at 28 µg/d then repeat schedule of assessments starting at D8. Refer to [Table 7-1](#) and [Table 7-2](#) for cohort Ia and [Table 7-3](#) and [Table 7-4](#) for cohort IIa/IIIa. In addition, at the start of blinatumomab cycle 2, subjects should resume the schedule of assessments following D85 to D110 procedures as outlined in [Table 7-1](#) for cohort Ia and [Table 7-3](#) for cohort IIa/IIIa (exception is for pembrolizumab specific tests which are referenced in [Table 7-2](#) and [Table 7-4](#)).

In addition to the events described above, the dose may be temporarily or permanently reduced if, by investigator's judgment, it is necessary for safety reasons.

After at least 7 days of dosing at the reduced level, the dose may be increased back to the next higher dose level. An infusion interruption of more than 14 days due to an adverse event related to blinatumomab will lead to permanent discontinuation of treatment. In case of logistical difficulties, restart of treatment can be postponed for up to 7 additional days without resulting in permanent treatment discontinuation. Treatment may be also interrupted or permanently discontinued at the discretion of the investigator if any clinical/laboratory adverse event is considered to be medically relevant.

In case of signs of cytokine release, dexamethasone must be administered orally or IV at a dose of at maximum 3 x 8 mg/day for up to 72 hours.

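### Protocol 6.2.1.4.1 opens with a temporary stop for every related grade 4 event, while Table 6-1 requires permanent discontinuation for grade 4 CRS, neurologic and other clinically relevant events, and no text says which prevails

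*Protocol*

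**What the plan says.** Protocol 6.2.1.4.1 opens with a general rule. For CTCAE v4.0 grade 4 events at least possibly related to blinatumomab, it requires that "blinatumomab be stopped until the adverse event has recovered to CTCAE grade 1 or baseline". No event type is excepted.

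Table 6-1 comes next. For grade 4 CRS, grade 4 neurologic events and grade 4 other clinically relevant adverse events, the whole instruction is "Permanently discontinue blinatumomab". For grade 3 events in the same three categories, the table gives a restart path: "Restart no less than 72 hours after the initial observation of the grade 3 event at the following dose levels". Those levels are 28 or 9 µg/day, depending on the dose at which the event occurred.

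The text after the table says that, when the infusion is restarted under the Table 6-1 guidelines, "the schedule of assessment procedures should be repeated to align with the re-started blinatumomab dose". It gives starting points for 9 and 28 µg/day only. It also sets a general limit: "An infusion interruption of more than 14 days due to an adverse event related to blinatumomab will lead to permanent discontinuation of treatment".

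Table 6-1 has a separate row for seizures of grade 2 or higher. It interrupts the drug, sets a wait of 7 days after the last seizure, and says "For restart, refer to grade 3 neurologic events above for dose level rules for re-instituting infusion". A permanent stop follows only if a second seizure occurs after re-initiation.

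**The concern.** The sentence and the table give different end-points for the same event. Under the sentence, a related grade 4 CRS that settles to grade 1 has met the condition that ends the stop. Under the table, the subject never receives blinatumomab again. The word 'until' makes the stop temporary on its natural reading, and the sentence does not defer to the table.

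What is at stake is subject safety: whether someone who has had a grade 4 CRS or neurologic event may be re-exposed. A stopping rule at that grade should have one meaning, and two sites should not be able to act differently and both cite the protocol.

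**Working it through.** No arithmetic applies. The check sets the opening sentence against each category of Table 6-1, and then looks for text that decides between them.

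| Table 6-1 category | Table instruction at grade 4 | Opening sentence | Result |
|---|---|---|---|
| CRS | Permanent stop | Stop until grade 1 or baseline | Conflict |
| Neurologic events | Permanent stop | Same | Conflict |
| Other clinically relevant events | Permanent stop | Same | Conflict, but only for events judged clinically relevant |
| Seizure, grade 2 or higher | No separate grade 4 line; interrupt, restart possible | Same | Broadly consistent with the sentence, but overlaps the grade 4 neurologic row |
| Elevated liver enzymes | Not graded; interrupt, with a permanent stop for a combined bilirubin or INR plus transaminase pattern | Same | Governed by its own criteria and Section 6.4 |

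Exactly three rows carry a grade 4 label, and all three require a permanent stop.

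**The third row.** Section 9.2.2.1 has all grade 3 and 4 laboratory values recorded as adverse events. A related grade 4 laboratory value that is not judged clinically relevant falls outside the third row. For that event the opening sentence applies without conflict and does useful work.

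**Text that might decide.**
- 6.2.1.4.1, after the table: describes restarts as made under Table 6-1 and gives schedules only for 9 and 28 µg/day, which are the table's grade 3 restart doses. This favours the table but states no precedence.
- The 14-day limit in the same text: caps the length of an interruption. A grade 4 event that recovers within 14 days meets the sentence's condition and stays barred under the table.
- 6.2.2.2.1 and footnote ll of Table 7-1: refer to Table 6-1 for interruptions. No precedence is stated.
- 6.2.3: requires discontinuation where protocol-specified safety criteria make it necessary. It does not say which criteria control when two disagree.

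The table is therefore the likelier operative rule, by inference only.

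**Seizure.** Appendix F lists seizures among the clinically relevant neurologic events. A grade 4 seizure therefore meets both the grade 4 neurologic row (permanent stop) and the seizure row (restart possible). Both rows are inside Table 6-1, so giving the table precedence over the sentence does not settle this case.

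**The case against.** The strongest reply is that the sentence sets a minimum. It says when blinatumomab must be off and never says that it may be resumed. A site that permanently stops after grade 4 CRS complies with both texts. The specific instruction sits directly below the general one, and the table offers no restart path in its three grade 4 rows. A site would have to pass over an explicit instruction to go wrong. Any restart must also be in hospital, with dexamethasone premedication. This reply lowers the practical risk and keeps the point minor. It does not remove the fault, because a stop that lasts until recovery is naturally read as ending at recovery.

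Three stronger readings are tempting, and the documents do not support them.

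- A reader might infer that grade 4 CRS or neurologic events get twice the recovery time of grade 3, by setting 14 days against the 7 days in the grade 3 conditions ("Initial grade 3 CRS does not improve to grade" 1 or less, and "Initial grade 3 neurologic event does not improve to grade" 1 or less, within 7 days). The two limits measure different things. The 14 days caps an infusion interruption for a related event of any grade, so it also applies after grade 3. The 7 days limits the time for the event to improve. No ratio should be drawn.
- A reader might infer that a full-dose restart after grade 4 is provided for, since the sentence names no restart dose. The restart text gives schedules only for 9 and 28 µg/day.
- A reader might infer an effect on DLT evaluability. In Appendix E, the exceptions for non-laboratory, non-hematologic toxicity are all grade 3, so a related grade 4 CRS or neurologic event in the DLT window is itself a DLT. Section 10.1.2.1 makes a subject with a DLT evaluable whatever dosing follows. For these events the effect is nil.

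**Conclusion.** The point holds as a minor one: a safety rule that is wrong as written. The opening sentence lacks an exception that Table 6-1 needs. The conflict is clear for two rows (CRS, neurologic) and partial for the third (other events, where judged clinically relevant). The grade 4 seizure overlap is real but is a separate ambiguity within the table and adds no weight to the main point.

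The conclusion rests on reading 'until' in its ordinary sense and on finding no text that ranks the sentence against the table. It does not claim that the protocol intends a restart after grade 4 CRS or neurologic events; the surrounding text points the other way. SAP Section 11 records that Part 2 will not proceed, so reach is limited to Part 1, planned at 6 to 30 subjects. The documents give no grade 4 rate, so the number of subjects affected cannot be stated.

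**What to change.** Keep the opening sentence of 6.2.1.4.1 and add 'unless Table 6-1 requires permanent discontinuation'. It then governs only related grade 4 events for which the table does not already require a permanent stop. Do not delete the sentence: that would remove the explicit stop for related grade 4 events outside the three rows.

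Separately, add one sentence to Table 6-1 saying whether a grade 4 seizure follows the grade 4 neurologic row or the seizure row. The choice is a clinical one for the sponsor.

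The cost is one clause and one sentence in an amendment or a site clarification letter, with no effect on sample size or analysis. The documents do not say whether any subject may still receive blinatumomab. If none will, one listing in the clinical study report would serve instead, showing for each related grade 4 event whether the drug was restarted (when and at what dose) or permanently stopped. SAP 10.6.2 and 10.6.8 already summarise events leading to interruption or withdrawal, and dose modifications with reasons, but not event by event at grade 4.
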